4.4.1.1.2 Maximum Overall Intensity

Maximum overall intensity will be derived from the daily intensities computed as described in Section 4.4.1.1.1 and is calculated as the maximum of the daily intensities over the period considered.

4.4.1.1.3 Presence

Presence is derived from the maximum overall intensity on the period considered:

- None: No presence
- Grade 1, Grade 2, or Grade 3: Presence
- Missing: Missing presence

Subjects with at least 1 non-missing presence for a specific endpoint will be included in the analysis. Conversely, those without a non-missing presence will not be included in the analysis of the endpoint.

4.4.1.1.4 Time of Onset

Time of onset is derived from the daily intensities computed as described in Section 4.4.1.1.1. It corresponds to the first day with intensity of Grade 1, Grade 2, or Grade 3.

Note: If a reaction is not continuous (i.e., reaction occurs over 2 separate periods of time intervened by at least 1 daily intensity Missing or None) then the time of onset is the first day of the first occurrence. For subjects who received 2 doses, the worst-case scenario will be used for the post-any dose summary (i.e., the shorter time to onset period will be used if present for both doses, or the available time to onset period will be used if present for either dose).

Categories for time of onset are as follows:

- D0–D3
- D4–D7

4.4.1.1.5 Number of Days of Occurrence

Number of days of occurrence over the period considered is derived from the daily intensities computed as described in Section 4.4.1.1.1. It corresponds to the number of days with daily intensities of Grade 1, Grade 2, or Grade 3. Number of days of occurrence on the solicited period with a specified intensity may also be derived. For subjects who received 2 doses, the worst-case scenario will be used for the post-any dose summary (i.e., the larger number of days will be used if present for both doses, or the available number of days will be used if present for either dose).

Categories for number of days of occurrence during the solicited period are as follows:

- 1–3 days
- 4–7 days
- 8 days

4.4.1.1.6 Overall Number of Days of Occurrence

If a reaction is ongoing at the end of the solicited period, then the overall number of days of occurrence is derived from the daily intensities and the stop date of the reaction after the end of the solicited period. The overall number of days of occurrence is:

- (stop date – last vaccination date) + (number of days of occurrence within the solicited period) – length of the solicited period + 1

If the stop date is missing or incomplete (contains missing data), the overall number of days of occurrence will be considered as Missing. For subjects who received 2 doses, the worst-case scenario will be used for the post-any dose summary (i.e., the larger number of days will be used if present for both doses, or the available number of days will be used if present for either dose).

Categories for overall number of days of occurrence are as follows

- 1–3 days
- 4–7 days
- ≥ 8 days
- Missing

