9.3.1.3.3 Unsolicited Adverse Events

In addition to recording solicited reactions, subjects or subjects’ parents/guardians will be instructed to record any other medical events that may occur from Visit 1 through Visit 2 (Diary Card 1) for all subjects and from Visit 2 through Visit 3 (Diary Card 2) for subjects receiving 2 doses of study vaccine. Space will be provided in the diary card for this purpose.

Information on SAEs will be collected and assessed throughout the study, from Visit 1 through Visit 2 for subjects receiving 1 dose of study vaccine, and from Visit 1 through Visit 3 for subjects receiving 2 doses of study vaccine.

Any SAE occurring at any time during the study will be reported by the Investigator in the CRB according to the completion instructions provided by the Sponsor; this includes checking the “Serious” box on the AE CRF and completing the appropriate Death/Safety Complementary Information CRFs. All information concerning the SAE is to be reported either as part of the initial reporting or during follow-up reporting if relevant information became available later (e.g., outcome, medical history, results of investigations, copy of hospitalization reports). See [Section 10](#) for further details on SAE reporting.

For each unsolicited AE (whether serious or non-serious), the following information is to be recorded:

- Start and stop dates^a
- Intensity of the event:

For measurable unsolicited AEs that are part of the list of solicited reactions, the size of the AE as well as the temperature for fever will be collected and analyzed based on the corresponding scale used for solicited reactions (see [Table 9.1](#), [Table 9.2](#), [Table 9.3](#), [Table 9.4](#), and [Table 9.5](#)).

^a The stop date of all related AEs will be actively solicited. For other events, the Investigator will provide the stop date when it becomes available. AEs for which no stop date was obtained during the course of the study will be considered as ongoing at the end of the study.

All other unsolicited AEs will be classified according to the following intensity scale:

- Grade 1: A type of AE that is usually transient and may require only minimal treatment or therapeutic intervention. The event does not generally interfere with usual activities of daily living.

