4.4.1.2.5 Duration

Duration is derived from the start and stop dates of the unsolicited non-serious AE provided in the clinical database:

- stop date of unsolicited non-serious AE - start date of unsolicited non-serious AE + 1.

The duration should be considered as missing only if 1 or both of the start and stop dates of the unsolicited non-serious AE is missing or partially missing. For subjects who received 2 doses, the worst-case scenario will be used for the post-any dose summary (i.e., the longer duration will be used if present for both doses or the available duration will be used if present for either dose).

Duration will be displayed by period as following:

- 1–3 days
- 4–7 days
- 8–14 days
- \geq 15 days
- Missing

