5.3.1.5 Start Date and Stop Date

Missing or partially missing start dates for unsolicited AEs will remain missing and not be imputed. If either the start or stop date is missing or partially missing, the time of onset will be considered to be missing. Nevertheless, unsolicited AEs with missing time of onset will be included in analyses according to the visit at which the AEs were collected.

Missing or partially missing stop dates for AEs (solicited reactions and unsolicited AEs) will remain missing and not be imputed.

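### When no complete stop date is ever obtained, the SAP codes duration as Missing even where recorded data fix the category, and the two-dose 'worst-case' rule can then report the shorter event

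*SAP*

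**What the plan says.** SAP 4.4.1.1.6 gives the overall length of a solicited reaction that outlasts the Day 0–7 diary period as (the quoted text begins after its opening bracket) "stop date – last vaccination date) + (number of days of occurrence within the solicited period) – length of the solicited period + 1". Without a usable stop date: "If the stop date is missing or incomplete (contains missing data), the overall number of days of occurrence will be considered as Missing". The categories are 1–3, 4–7 and ≥ 8 days, plus Missing.

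SAP 4.4.1.2.5 applies the same idea to unsolicited non-serious AEs: "The duration should be considered as missing only if 1 or both of the start and stop dates" is missing or partial. Its top category is ≥ 15 days, again with a Missing row. SAP 4.4.1.3.3 carries this over to SAEs by reference. SAP 5.3.1.5 closes the door on any substitute: "Missing or partially missing stop dates for AEs (solicited reactions and unsolicited AEs) will remain missing and not be imputed".

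For children who receive two doses, the post-any-dose summary takes what the SAP calls the worst case. For solicited reactions this is the larger number of days when both doses have one, "or the available number of days will be used if present for either dose". For unsolicited AEs, "the longer duration will be used if present for both doses or the available duration will be used if present for either dose".

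The protocol gives events without a stop date a status, in the footnote to 9.3.1.3.3: "AEs for which no stop date was obtained during the course of the study will be considered as ongoing at the end of the study". Neither SAP duration list has a category for that status. SAP 4.4.1.1.7 does define an ongoing reaction, but only at the end of the solicited period.

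**The concern.** The absence of a stop date is unlikely to be unrelated to how long an event lasts. An event that settles into a stable or chronic course is a natural candidate for never receiving one. Coding it as Missing takes it out of the top duration category, even when the diary or the last visit already shows that it belongs there.

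The two-dose rule adds a second problem. In a per-dose table the unknown duration at least appears as Missing. In the post-any-dose summary it is overwritten by the other dose's value, which may be much shorter, under a rule meant to be conservative.

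Duration is a listed endpoint for unsolicited AEs (Protocol 9.3.1.2, item 4) and immediate AEs (item 1). For solicited reactions the listed endpoint is the number of days of occurrence within Day 0–7, so the overall count in SAP 4.4.1.1.6 goes beyond it. Duration is not listed for SAEs.

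**Working it through.** The documents state no figure on this point that could be reproduced, so the check applies the SAP's rules to the visit schedule.

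**Inputs**
- Solicited period: Day 0 to Day 7, which is 8 days (SAP 3.2).
- Last visit: Day 21–28 for adults (SAP Table 3.2); 28–35 days after the final dose for children (SAP Table 3.1).
- k: number of diary days with a reaction of Grade 1 or more.
- S: days from the last vaccination to the stop date.

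**1. Formula check.** Overall days = S + k − 8 + 1.
- Onset Day 7, stop Day 8: 8 + 1 − 8 + 1 = 2, correct.
- Present every day from Day 0, stop Day 10: 10 + 8 − 8 + 1 = 11, correct.

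The formula is sound; the issue is only what happens when S is unknown.

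**2. Minimum length of a solicited reaction with no stop date.** Replace S by the last day on which the reaction is documented as present, using the earliest day of the visit window.
- Present on all 8 diary days and ongoing: at least 8 days from the diary alone.
- Adults, still present at Day 21: from 21 + 1 − 8 + 1 = 15 days (k = 1) to 21 + 8 − 8 + 1 = 22 days (k = 8).
- Children, still present at Day 28: from 28 + 1 − 8 + 1 = 22 days (k = 1) to 28 + 8 − 8 + 1 = 29 days (k = 8).

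Every case belongs in '≥ 8 days'. The SAP rule returns Missing for each.

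**3. Minimum length of an unsolicited AE.** Duration = stop − start + 1. For an AE documented as unresolved at a last visit on Day L, '≥ 15 days' is certain when L − onset + 1 ≥ 15, that is, onset ≤ L − 14.
- Adults, L = 21: onset by Day 7 (21 − 7 + 1 = 15). With onset on Day 8–21 the category is not determined.
- Children after the final dose, L = 28: onset by Day 14 (28 − 14 + 1 = 15). With onset on Day 15–28 it is not determined.

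**4. Two-dose rule.** Take a child whose dose-1 reaction lasts 2 days. The dose-2 reaction is recorded on all 8 diary days, continues, and never gets a stop date. I assume that the overall count for a reaction ending within the diary period equals its diary count, which the category list implies but the SAP does not state.
- SAP 4.4.1.1.5, post-any-dose: the larger of 2 and 8 is 8, so '8 days'.
- SAP 4.4.1.1.6, post-any-dose: dose 2 is Missing, the available value is 2, so '1–3 days'.

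The overall duration is then shorter than the in-period duration for the same child and reaction. With a recorded dose-2 length of 29 days the second line would give '≥ 8 days'. If 'present' in the rule means that the reaction (not the value) is present at both doses, the larger of Missing and 2 is undefined. Either reading needs repair.

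**5. Size.** One subject is 1/60 = 1.7 points in an adult group or 1/30 = 3.3 points in a child group. The documents give no count of such events. As an illustration only, assume 1 to 3 affected subjects per group, no resolved reaction of 8 days or more, and the planned group size as denominator, with Clopper-Pearson 95% intervals for '≥ 8 days':
- n = 30: 0% (0–11.6) under the SAP; 3.3% (0.1–17.2) to 10.0% (2.1–26.5) when classified by minimum duration.
- n = 60: 0% (0–6.0) under the SAP; 1.7% (0.0–8.9) to 5.0% (1.0–13.9) when classified by minimum duration.

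**The case against.** A reader might infer that any event unresolved at the last visit is tabulated as Missing. The documents do not support that. The trigger is a stop date that is never obtained. The same footnote in Protocol 9.3.1.3.3 has stop dates of related AEs actively sought. Protocol 5.1.4 and 9.3.1.3.5 follow related events beyond the subject's participation, and Protocol 9.3.1.1 counts every solicited reaction as related. Many late stop dates should therefore arrive. The exposure that remains is real but narrower: follow-up may end when an event is merely stable or chronic, unrelated AEs get a stop date only if one becomes available, and follow-up can fail.

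A reader might also infer that a blank stop date means the event was present at the last visit, so that a minimum duration always follows. It does not. The protocol's convention labels such AEs ongoing, but for an unrelated AE a blank may simply mean that resolution was not recorded. Using that label to fill '≥ 15 days' would create the opposite bias.

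Other points stand. Per-dose and single-dose tables show a Missing row, occurrence and intensity do not depend on the stop date, and the analysis is descriptive throughout. The solicited endpoint listed in the protocol is served by SAP 4.4.1.1.5, which needs no stop date. The two-dose problem is confined to children given two doses, a subset of the 60 planned in Groups 1 and 2.

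None of this answers the two specific defects: a category known from the diary or visit record is discarded, and a worst-case rule can return the better case.

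**Conclusion.** The point holds in this limited form. Where no complete stop date is ever obtained, SAP 4.4.1.1.6 and 4.4.1.2.5 give Missing even when recorded data settle the category, and the two-dose rule can replace that Missing with a shorter duration that contradicts SAP 4.4.1.1.5.

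The diary-only case and the two-dose contradiction follow from the rules as written, subject to the reading of the two-dose rule set out in the working. The 15- and 22-day minima, and the Day 7 and Day 14 onset limits, also require that the event be documented as present at the last visit and that the visit fall within its window.

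The size is unknown because no count is given: each affected subject is worth 1.7 points of 60 or 3.3 points of 30. A claim that the top category is understated in every group would go too far. No group need contain such an event, and partial dates can affect short events as well.

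**What to change.** In SAP 4.4.1.1.6 and 4.4.1.2.5 (and so in 4.4.1.3.3 by reference):
- When an event is documented as ongoing and has no stop date, compute its minimum duration from the diary days and the last visit or contact at which it was recorded as present. Assign the top category if the minimum reaches it; otherwise show 'Ongoing at end of study'.
- Keep Missing for an unknown start date or unknown resolution status. Do not infer ongoing from a blank stop date alone.
- In the two-dose rule, let an ongoing event outrank a resolved one, do not let a shorter available value replace a Missing one, and say whether 'present' refers to the reaction or to the value.
- Add a line to SAP 5.3.1.5 that this classification does not impute a stop date.

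The cost is a few lines of text and one derivation. Diary days and visit dates are already collected, and SAP 4.4.1.1.7 already derives ongoing status after Day 7. The documents do not show a field recording resolution status at the last visit, so the sponsor should confirm one exists; without it, only the diary-based part can be applied. The small downside is that the top duration category becomes slightly less favourable.

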4.4.1.1.7 Ongoing

Ongoing is derived from the last daily intensity of the solicited period computed as described in Section 4.4.1.1.1 and the maximum intensity on the ongoing period. The investigator’s ongoing flag is not used because the measurement would determine the ongoing status of the reaction.

Note: The intensity could be considered None (not a reaction) in the analysis despite being considered a reaction by the investigator (e.g., swelling measurement > 0 mm but < 25 mm in adults). If the last daily intensity of the solicited period is at least Grade 1 and maximum intensity on the ongoing period is also at least Grade 1, then the reaction is considered ongoing. In any other cases, the reaction will not be considered as ongoing.

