4.4 Derived Endpoints: Calculation Methods

4.4.1 Safety

4.4.1.1 Solicited Reactions

4.4.1.1.1 Daily Intensity

All daily records for solicited reactions will be derived into daily intensity according to the following classification: None, Grade 1, Grade 2, Grade 3, or Missing.

For measurable injection site reactions (erythema/swelling):

- For subjects 6 months to < 9 years of age
 - Grade 1: > 0 to < 25 mm
 - Grade 2: ≥ 25 to < 50 mm
 - Grade 3: ≥ 50 mm
- For subjects 18 years of age and older
 - Grade 1: ≥ 25 to ≤ 50 mm
 - Grade 2: ≥ 51 to ≤ 100 mm
 - Grade 3: > 100 mm

For measurable systemic reactions (i.e., fever):

- For subjects 6 months to < 36 months of age
 - Grade 1: $\geq 38.0^{\circ}\text{C}$ to $\leq 38.5^{\circ}\text{C}$, or $\geq 100.4^{\circ}\text{F}$ to $\leq 101.3^{\circ}\text{F}$
 - Grade 2: > 38.5°C to $\leq 39.5^{\circ}\text{C}$, or > 101.3°F to $\leq 103.1^{\circ}\text{F}$
 - Grade 3: > 39.5°C , or > 103.1°F

- For subjects 3 to < 9 years of age and 18 years of age and older
Grade 1: $\geq 38.0^{\circ}\text{C}$ to $\leq 38.4^{\circ}\text{C}$, or $\geq 100.4^{\circ}\text{F}$ to $\leq 101.1^{\circ}\text{F}$
Grade 2: $\geq 38.5^{\circ}\text{C}$ to $\leq 38.9^{\circ}\text{C}$, or $\geq 101.2^{\circ}\text{F}$ to $\leq 102.0^{\circ}\text{F}$
Grade 3: $\geq 39.0^{\circ}\text{C}$, or $\geq 102.1^{\circ}\text{F}$

For the derivation of daily intensities, the following sequential steps will be applied:

- 1) Solicited reactions (except fever/pyrexia) with an investigator presence recorded as “No” and with all daily records missing then all daily intensities will be derived as None.
- 2) For a temperature partially missing after decimal point, the data will be analyzed replacing “MD” (missing data) by zero. For example, a “39.MD” daily temperature will be considered as “39.0°C” at the time of analysis.
- 3) For non-measurable solicited reactions, the daily intensities will correspond to the daily records reported in the clinical database. For measurable solicited reactions, the daily measurements reported in the clinical database will be converted based upon the intensity scales defined in the protocol; this assumes that a reaction that is too large to measure (non-measurable, “NM”) is Grade 3. Note the intensity could be considered “None” (not a reaction) in the analysis despite being considered a reaction by the investigator (e.g., swelling measurement > 0 mm but < 25 mm in adults).

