Note: The maximum intensity on the ongoing period is derived from the record of the maximum intensity/measurement after the end of the solicited period following the rule described above.

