5.3 Handling of Missing Data and Outliers

5.3.1 Safety

No imputation of missing data will be conducted. All subjects with safety data and all safety data recorded in the CRFs will be included in the safety analyses. No search for outliers will be performed. In all subject listings, partial and missing data will be clearly indicated as missing.

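### SAP 4.4.1.1.7 treats a missing Day 7 or post-Day-7 intensity as resolution, so a solicited reaction can lose its ongoing status and its recorded stop date goes unused

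*SAP*

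**What the plan says.** SAP 4.4.1.1.1 derives each daily record "according to the following classification: None, Grade 1, Grade 2, Grade 3, or Missing". For the time after Day 7 it adds: "The maximum intensity on the ongoing period is derived from the record of the maximum intensity/measurement after the end of the solicited period". It gives no rule for a single blank on Day 7 or for a blank post-Day-7 record. SAP 5.3.1.4, on missing solicited intensities, only refers back to 4.4.1.1.1.

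SAP 4.4.1.1.7 then sets the status. Its test for ongoing has two parts, with Grade 1 as the threshold in each: "If the last daily intensity of the solicited period is at least Grade 1 and maximum intensity on the ongoing period is also at least" (the sentence goes on to name that grade). Every remaining combination falls under one clause: "In any other cases, the reaction will not be considered as ongoing". On the investigator's own record of continuation, the section states: "ongoing flag is not used because the measurement would determine the ongoing status of the reaction".

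The status controls whether the stop date is used. SAP 4.4.1.1.6 opens: "If a reaction is ongoing at the end of the solicited period, then the overall number of days of occurrence is derived". The inputs it names are the graded days and the date on which the reaction stopped. The section does not say what the overall number of days is for a reaction that is not ongoing. If the stop date itself is missing or incomplete, the overall number of days is set to Missing.

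**The concern.** A blank is not evidence that a reaction ended, yet the catch-all clause gives it the same consequence as a recorded None. The reason offered for setting the investigator's flag aside is that the measurement decides. That is sound when a measurement exists: adult swelling below 25 mm is not a reaction for analysis, whatever the flag says. It gives no guidance when nothing was recorded, and pain, tenderness, headache, malaise and myalgia are graded without any measurement.

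The treatment is also uneven. A missing stop date leads to a Missing category, while a missing intensity leads to a definite negative, even when a complete stop date shows that the reaction lasted beyond Day 7.

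At stake are two derived outputs: ongoing status, and the overall number of days of occurrence with its top category of 8 days or more. A blank can take a reaction out of the ongoing class but can never put one in, so any effect on the description of lasting reactions goes in one direction.

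**Working it through.** **Inputs.** Five intensity values (SAP 4.4.1.1.1); the two-part condition (4.4.1.1.7); the overall-days formula and its categories 1-3, 4-7, 8 or more, and Missing (4.4.1.1.6); a solicited period of Day 0 through Day 7, that is 8 days (Protocol 9.3.1.3.2).

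**Step 1: the rule over all combinations.** Day 7 intensity by post-Day-7 maximum gives 5 x 5 = 25 cells.
- Both at least Grade 1: 3 x 3 = 9 cells, ongoing.
- All others: 25 - 9 = 16 cells, not ongoing.
- Cells with at least one Missing: 25 - 4 x 4 = 9, all not ongoing.
- Of these 9, two pair Missing with None, where not ongoing is defensible. The other 7 contain no recorded None, and there the negative has no recorded basis.

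**Step 2: the formula itself is sound.** For a continuous reaction with onset on Day k and stop on Day s (8 or later), graded throughout, the solicited count is 8 - k. Overall days = s + (8 - k) - 8 + 1 = s - k + 1, which is the true duration. The problem is only whether the formula is reached.

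**Step 3: examples with stop date Day 14.** The last column assumes that a non-ongoing reaction keeps its solicited-period count; the SAP does not say so.

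| Onset | Blank value | Formula, if the stop date were used | Count left if not ongoing |
|---|---|---|---|
| Day 5 | post-Day-7 maximum | 14 + 3 - 8 + 1 = 10 (8 or more) | 3 (1-3) |
| Day 5 | Day 7 | 14 + 2 - 8 + 1 = 9 (8 or more) | 2 (1-3) |
| Day 1 | post-Day-7 maximum | 14 + 7 - 8 + 1 = 14 (8 or more) | 7 (4-7) |
| Day 0 | post-Day-7 maximum | 14 + 8 - 8 + 1 = 15 (8 or more) | 8 (8 or more) |

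The last row shows the limit: with all of Days 0 to 7 graded and only the later grade blank, the category does not change.

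**Step 4: how many patterns change category.** Take onset Day 0 to 7 and stop Day 8 to 14, which is 8 x 7 = 56 patterns. On the same fallback assumption the category is shortened in 40 of 56 when the post-Day-7 value is blank, and in 52 of 56 when Day 7 is blank. These patterns are equally weighted. They show that the effect is not confined to one contrived case, but they are not expected frequencies.

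**Step 5: weight of one subject.** With the planned group sizes, 1/60 = 1.7 percentage points in Groups 3 to 5 and 1/30 = 3.3 points in Groups 1 and 2.

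**The case against.** **The affected variable is secondary.** The protocol endpoint is the number of days of occurrence for reactions from Day 0 through Day 7. SAP 4.4.1.1.5 derives it from graded days alone, and SAP 5.1.3.1 lists that variable for presentation, not the overall number of days. This stands. A reader might infer that the protocol endpoint is shortened. It is not: in the Day 5 to 7 pain example it is 3 days with or without the later grade.

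**The fallback is inferred.** SAP 4.4.1.1.6 is silent on non-ongoing reactions. This stands too: 3 days is a consequence under an assumption, not a stated result.

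**There is no clear breach of the missing-data rules.** A reader might set the rule against "No imputation of missing data will be conducted" (SAP 5.3.1) or against "Missing: Missing presence" (4.4.1.1.3). Neither gives a firm contradiction. The SAP uses other classification conventions alongside its no-imputation statement: a missing immediate field is taken as later than 20 minutes (5.3.1.1), and missing causality is taken as related (5.3.1.2). The presence rule concerns a different variable, and a reaction graded on Days 5 to 7 is present under it. The weakness of 4.4.1.1.7 is that its stated reason does not cover a missing value.

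**Blanks may be few.** Sites clarify incomplete diary entries (Protocol 11.1 and 13.2), computerized checks look for omissions (11.2), and a statistical review precedes database lock (SAP 5.6). The case report form is not in the documents, so whether a stop date can be stored without a grade is unknown. This limits the size of the effect, not the logic.

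**Restoring the flag would do harm.** With Day 7 blank, later adult swelling recorded as 10 mm and a flag of yes, a general override would make a recorded non-reaction ongoing. This stands and shapes the fix.

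**Conclusion.** The point holds in a limited form. As written, a missing Day 7 or post-Day-7 intensity is classed as not ongoing, and a complete later stop date is then left out of the overall number of days. This concerns 7 of the 25 intensity combinations, and in each of them the error can only remove an ongoing status.

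The documents do not support the wider reading that continuing reactions in general are reported as short. The Day 0 to Day 7 count is unaffected. A reaction graded on all 8 days stays in the top category if only the later grade is blank. The shortening from 10 to 3 days rests on the assumed fallback. Nor is ignoring the flag wrong in itself; it is justified wherever a value is recorded.

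The overall size is unknown, because the documents give no rate of blanks and it may be low. In groups of 30 or 60, a single case is visible in a table. It is a small gap in a descriptive study, worth closing before database lock because the repair is cheap.

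**What to change.** In SAP 4.4.1.1.7:
- Keep not ongoing if either recorded value is None. This preserves the rule for small adult swelling.
- If one or both values are Missing and neither is None, do not class the reaction as not ongoing.
  - For reactions without a measurement (for example pain or tenderness, headache, malaise, myalgia), treat it as ongoing and apply 4.4.1.1.6 when a stop date after Day 7 is recorded.
  - Otherwise, and always for erythema, swelling and fever, where size or temperature decides, report Ongoing and the overall number of days as Missing.

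In SAP 4.4.1.1.6, state that the overall number of days equals the solicited-period count for reactions that are truly not ongoing.

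When this is programmed, check against the case report form that a post-Day-7 maximum counts as Missing only where one was due. A reaction that the site recorded as ended by Day 7 has no later value to give and should stay not ongoing.

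Cost: a few sentences and one programming condition, with no new data. The downside is that a few durations become longer or Missing. Where Day 7 itself is blank, the formula does not count that day, as in the 9-day example above.
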